NCT02403817 Training Attention and Eye Movement in ASD 8/8/2019

Study Protocol and Statistical Plan

Current therapies for Autism Spectrum Disorder (ASD) target social and language behaviors, but due to the highlevel nature of these skills any improvement rarely extends beyond the targeted behavior. This project uses new technology to implement a novel concept for behavioral intervention to improve basic attention and eye movement skills in ASD. Children will play gaze-driven video games at home during the intervention, receive pre- and post-training assessment of attention, and eye movement function. Because these basic skills form the foundation for good social communication, training these abilities has the potential to improve a broad spectrum of clinical symptoms, and in young children may affect the course of development.

This is a pilot project with a small clinical trial. The aims are:

1: Conduct video game training system with 2 groups of 20 ASD children/teens/young adults (aged 9-26).

2: Evaluate efficacy of training using 3 levels of outcome measures for pre- and post- testing and followup. Level 1 will be a direct test of attention and eye movement. Level 2 will test attention and eye movement function in a digital environment. Level 3 will test the effect of training on social skills measured by questionnaires and in a live social interaction.

Research Design and Methods

We will recruit 40 male and female children with ASD (ages 9-26) to participate in the clinical trial. Participants will meet the criteria for Inclusion and Exclusion described below (we have an existing pool of potential participants that meet inclusion criteria, but expect to screen 50 children to find 40 that meet study criteria).

Collaborator [name] (Rady Children's Hospital) will be responsible for diagnosis of participants who do not already have required diagnostic assessment. [name] is the Clinical Director Rady Children's Hospital Autism Discovery Institute (ADI). [name] is ADI-R and ADOS reliable and is a certified trainer for both instruments. ASD participants will be recruited by [name] through ADI. We also have a large pool of children and teens with ASD from previous studies who meet diagnostic standards, the majority of whom will be willing to participate in the proposed project.

General inclusion/Exclusion criteria:

- 1. All participants must be cooperative and able to follow instructions.

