Intervention Phase: During this 8-week period, study participants will be asked to play a video game at home for a minimum of 30 minutes per day, 5 times per week. Parents/caregivers will oversee the daily in-home training and will be briefed along with the subjects at Session 2. Participants (and parents) will be phoned during the first 3 days of in-home testing to assure that there are no problems with equipment or use of equipment. Participants will return to our lab at 4 weeks, for an abbreviated round of tests (Level 1, to assess attention and eye movement, described below). Game play will be monitored as in our pilot testing using a secure 'dropbox' through which we will receive daily summaries of the amount of time each child has played the games, amount of time spent in calibration, and notes from the child regarding any problems or comments they might have about the games. If we find that a child is not playing the required amount of time, or has excessive calibration time, we will contact the family and follow-up with a home visit to assess the problem if necessary. This system worked very well for us in the pilot testing. Children who withdraw (or whose participation is terminated for failure to play the games) from the study will be replaced. An investigator from the project will always be available to troubleshoot any hardware/software problems, and discuss the child's progress by phone, e-mail, or in-home visits as required.

Final Evaluation Phase At the 8 week lab visit (the end of the intervention period), we will collect postintervention assessment at three outcome levels (direct testing of attention and eye movement and social questionnaires; simulation task testing; real social interaction-- all described below). We will ask trainees and their parents to complete a questionnaire evaluating their experience with particular focus on the ease of use of the equipment and game and the enjoyability of the training game.

Attention/Eye Movement Tests: The following tasks are a direct test of improvement of spatial attention disengagement and orienting and eye movement accuracy and initiation speed.

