Spatial Attention Task (E-Task): This task is patterned after Posner's classic cued spatial attention tasks, but uses target discrimination rather than detection. The task display is a central fixation cross on a computer monitor flanked by boxes on the left and right. Trials begin with either an attention directing cue (one of the boxes brightened) or a null cue (no change or both boxes brightened). Following a short (100 ms) or long (800 ms)

delay, a target (letter "E" pointing up, down, left or right) is presented in either the cued (valid) or the opposite uncued (invalid) location. The subject moves a joystick lever to indicate target orientation (up, down, left, right). Results from a number of studies using this task demonstrate slowed disengagement and shifting of attention in ASD children and adults. A study that used this task to examine spatial attention development in typically functioning children and adults will provide estimates of typical behavior on this task.

Analysis: Measures to be used from this task are: attention disengagement index (difference between accuracy to cued and uncued targets); attention orienting index (difference between cued targets with short vs. long attention orienting delays)³. Analyses for pilot testing to assess improvement in attentional skills will test the disengagement and orienting indices to: 1) compare individual participants against control performance (using means and variability from age-matched typical controls at pre- and post-testing ⁸. Simple analyses will use a t-test or repeated measures ANOVA to examine attention differences in pre- and post- measures and group differences and interactions.

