Gap-Overlap Saccade Task: The Gap-Overlap saccade task is a classic oculomotor paradigm during which a participant's inclination to "get stuck" on an available fixation target is assessed. Each trial starts with a fixation cross at the center of the screen and a single target drawn randomly from 16 possible peripheral locations appears either synchronously with the offset of fixation (baseline condition), 400 ms after the offset of fixation (gap condition), or does not disappear at all (overlap condition). The participant is instructed to look directly at the target when it appears as quickly as possible. The difference between saccade latency in the gap and overlap conditions provide an index of gaze and attention disengagement. Studies from our lab in ASD adolescents and teens found large and significant differences with a longer (400 ms) gap duration⁷. In addition, the spatial accuracy measured to the peripheral targets in this task was significantly lower for ASD versus typically-developed adolescents and teens.

Analysis: Measures to be used from this task are: saccade latency (time to initiate a saccade to a target), saccade accuracy (degrees error of saccade to the target), time to disengage attention/gaze (difference between saccade latency in overlap compared to gap condition). Analyses for pilot testing to assess improvement in eye movement skills use these measures and are the same as those described above for spatial attention task. Simple analyses will use a t-test or repeated measures ANOVA to examine eye movement differences in pre- and post- measures and group differences and interactions.

Anti- Saccade Task: Measures of fixation variability from this anti-saccade task provide an assessment of response to distraction and so serve as a secondary measure of efficacy of the training intervention's targeted skill. The ability to maintain steady fixation is related to resistance to distraction and engages the frontal circuits involved in distraction suppression. Children and adults with ADHD symptoms who have difficulty suppressing distraction typically show difficulty maintaining steady fixation during an extended (1500ms) interval. This finding is consistent with disrupted fronto-striatal circuitry in ADHD and with animal work showing the role of fronto-striatal circuits in saccade suppression. Our results from previous work showing a decrease in fixation instability after training, suggest that our games improve resistance to distraction.

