From these analyses, it is possible to determine the degree to which participants respond appropriately, both linguistically and behaviorally to social interactive cues. We will examine both speech and non-verbal indications of engagement, such as gaze and gestures. This high level outcome measure allows us to examine the subtleties of social engagement during a conversation. We expect that post-intervention improved attention and eye movement will promote more effective social interaction.

Statistical Plan

All outcome testing will be done before training then repeated after training completion.

Level 1 (and Screening for entry criteria): The first level will use tests we have developed and published to directly test whether the speed, accuracy, and spatial breadth of eye movements and attention have improved. These tasks will be used to screen participants for presence of attention and eye movement deficits and will be used as a direct test of improvement of spatial attention disengagement and shifting and eye movement accuracy and initiation speed.

Measures to be analyzed (indices of attention orienting and disengagement, saccade accuracy, latency and gaze/attention) disengagement are described above as are analyses to evaluate effects at the single case level. Analyses will evaluate treatment outcome and differences in outcome between the two groups. A multivariate analysis (MANOVA) will provide a global (linear vector) comparison of all outcome measures at preand post-testing points for the two groups (i.e., differences in all measures between pre- and post-testing and between groups). Repeated measures ANOVAs for each of the five outcome measures will test improvement over time (slope > 0) and trends (linear, non-linear), and differences between groups in these effects. Level 2: The second level will use a driving simulation to test how well the trainee can negotiate a simulated environment with a variety of obstacles (i.e., test improvement in attentional and visual monitoring and speed and accuracy of response).

Simple analyses will compare (repeated measures ANOVA to examine differences in pre- and post-measures and group differences and interactions).

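### Level 1 plans the gaze-versus-joystick contrast but does not make it the test that decides efficacy, although a shared practice gain alone can make the time effect significant

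*Combined protocol and SAP*

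**What the plan says.** Aim 2 of the combined protocol and SAP is to "Evaluate efficacy of training using 3 levels of outcome measures for pre- and post- testing and followup". The Statistical Plan, Level 1, states the purpose of the analyses as two parallel targets: "Analyses will evaluate treatment outcome and differences in outcome between the two groups". It then describes a MANOVA covering pre-post and between-group differences, followed by a separate ANOVA per measure, described thus: "the five outcome measures will test improvement over time (slope > 0) and trends (linear, non-linear), and differences between groups in these effects".

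The E-Task section offers a choice of methods: "Simple analyses will use a t-test or repeated measures ANOVA to examine attention differences in pre- and post- measures and group differences and interactions". The Gap-Overlap and Anti-Saccade sections say much the same. Comparisons of individual participants with typical controls are also planned; the Level 1 text calls them "described above as are analyses to evaluate effects at the single case level".

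The Intervention Phase adds a Level 1 visit between baseline and the 8-week assessment: "Participants will return to our lab at 4 weeks, for an abbreviated round of tests". Under Assessment/Orientation Phase, children are assigned so that the two groups have equivalent mean and range on the attention and eye movement scores. Randomisation is not mentioned.

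No section ranks these analyses or says which result decides efficacy.

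**The concern.** The design has a useful comparator: Group 2 plays the same games with a joystick instead of gaze. Its value lies in the between-group comparison. A change from baseline within a group, or pooled over groups, mixes any training effect with whatever repeated testing produces by itself. If the time effect is significant and the group difference is not, the plan does not say what may be concluded about Aim 2. The reader of the results could not tell whether that conclusion was fixed in advance or chosen afterwards.

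**Working it through.** The plan gives no significance level, sidedness, SD, test-retest correlation or power, so it has no figure to reproduce. What follows is an illustration.

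**From the documents.** Two groups of 20, 40 in all (Aim 1). Level 1 testing at baseline, 4 weeks (abbreviated) and 8 weeks. Assignment balanced on baseline scores.

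**Assumed.** Two-sided 5% tests. Test-retest correlation r = 0.7 (range 0.6 to 0.9). Equal SD at both visits. No selection on baseline. No training effect. A retest gain of 0.2 baseline SD in both groups.

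**1. Pre-post test.** The SD of change is sqrt(2(1 - r)) = sqrt(0.6) = 0.775 baseline SD. The standardised gain is 0.2/0.775 = 0.258. The noncentrality is 0.258 × sqrt(n), which is 1.15 for n = 20 and 1.63 for n = 40. The noncentral t distribution gives the chance of rejection:

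| r | Shared gain (baseline SD) | One group, n = 20 | Pooled, n = 40 |
|---|---|---|---|
| 0.6 | 0.2 | 0.158 | 0.281 |
| 0.7 | 0.1 | 0.085 | 0.125 |
| 0.7 | 0.2 | 0.195 | 0.357 |
| 0.7 | 0.3 | 0.376 | 0.666 |
| 0.9 | 0.2 | 0.476 | 0.788 |

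**2. Three visits.** For weeks 0, 4 and 8 the linear trend weights are -1, 0, +1. With its own error term, the linear trend is therefore the pre-post test. The omnibus time F test, simulated with the gain rising evenly to 0.2 SD and equal correlations, rejects 0.156 (one group) and 0.284 (pooled) at r = 0.7. Over r = 0.6 to 0.9 the ranges are 0.125 to 0.386 and 0.216 to 0.696. This step assumes that the measure is taken at 4 weeks, which the abbreviated visit does not guarantee.

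**3. Group contrast, equal practice.** The shared gain cancels: (gain + effect 1) - (gain + effect 2) = effect 1 - effect 2. Without matching, the test on change scores rejects 5%. Suppose instead that children are closely matched on the analysed score (simulated as adjacent pairs split at random):
- the change-score test rejects 2.9%, 3.4% and 4.4% at r = 0.6, 0.7 and 0.9;
- the baseline-adjusted comparison rejects 5.0%, 5.0% and 4.9%.

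**4. Detectable difference, 80% power, 20 versus 20.**
- Change scores: 0.909 × sqrt(2(1 - r)) = 0.909 × 0.775 = 0.70 baseline SD at r = 0.7 (0.81 at r = 0.6, 0.41 at r = 0.9).
- Baseline-adjusted: 0.910 × sqrt(1 - r²) = 0.910 × 0.714 = 0.65 at r = 0.7 (0.73 at r = 0.6, 0.40 at r = 0.9).

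**5. If practice is not equal.** If practice differs between groups by 0.2 baseline SD, the unmatched change-score contrast rejects 12.5% at r = 0.7 (10.6% to 28% over the range).

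**The case against.** The strongest reply is that a group comparison or interaction is already planned for every task and at all three levels. What is missing is a ranking; no test is wrong. That stands. The documents also call the work a pilot, and they describe two intervention groups without labelling Group 2 a control. Both groups play games that are meant to shape attention, so part of a shared gain could be a real effect of the games, and the sponsor may reasonably report it. That also stands, but a time effect cannot separate such an effect from practice, and Aim 2 is stated in terms of efficacy.

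Three stronger readings are tempting, and the documents do not support them.
- A reader might infer that the sponsor will call a shared gain efficacy. The plan never says so; it is silent.
- A reader might take the Anti-Saccade remark, "Our results from previous work showing a decrease in fixation instability after training, suggest that our games improve resistance to distraction", as showing how this trial will be interpreted. It is rationale from earlier work whose design is not given.
- A reader might conclude that a positive slope is the wrong hypothesis for latency, degrees of error and disengagement time, which improve downwards. The sentence speaks of improvement, so improvement coding is a fair reading, and an F test does not depend on sign. This is a matter of wording.

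**Conclusion.** The point holds as a missing decision rule. Under the stated assumptions, a practice gain of 0.2 baseline SD with no training effect gives a significant time effect in about 20% of trials for one group (16% to 48% over r = 0.6 to 0.9) and 36% pooled (28% to 79%). The group contrast stays at or below about 5%. The correlation and the gain are assumptions, and the percentages move with them.

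The contrast has limits of its own. Assignment is described as score-balanced, with no mention of randomisation, so the contrast removes shared practice only if the groups are otherwise comparable. The 3.4% for unadjusted change is a limiting case: it assumes close matching on the analysed score and a random split within pairs, and the documents describe neither. Practice may also be unequal on the E-Task, where "The subject moves a joystick lever to indicate target orientation (up, down, left, right)" and only Group 2 trains with a joystick. That is a separate matter of interpretation, and it does not favour the time effect.

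**What to change.** Add to the Statistical Plan, Level 1: *Efficacy of gaze-driven training is decided by the two-sided difference between Group 1 and Group 2 at 8 weeks on each measure, adjusted for the baseline score of that measure. Time effects within or pooled over groups, pre-post t-tests and single-case comparisons are descriptive.* The adjustment follows from forming the groups on baseline scores. It keeps the test near its nominal 5% under matching and lowers the detectable difference from 0.70 to 0.65 baseline SD at r = 0.7. As a minor wording change, say that scores are coded so that a positive slope means improvement.

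This takes a few sentences and no new data or visits. There are two costs. Gains common to both groups, which may include a real effect of the shared games, can no longer be claimed as efficacy. And with 20 per group, 80% power is reached only for about 0.65 baseline SD (0.73 at r = 0.6, 0.40 at r = 0.9), so the pilot may be inconclusive. The sentence does not settle multiplicity: five independent tests at 5% give 1 - 0.95^5 = 0.23 for at least one false positive, so the sponsor should also say how the five results will be read together.

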Social Interaction Task: The third level of outcome assessment will test change in social behavior measured by questionnaires (SRS) and a live social situation between the research participant and a tester. Trainees will be engaged in an interactive conversation in which the tester uses a scripted conversation or games and set of cues to direct attention and eye movement. The script will involve several explicit and implicit redirections of attention and eye movement during the conversation between participants, using props in some cases to guide attention and gaze. Eye movements during the interaction will be measured with a lightweight eye-tracker worn by both participant and tester (based on a tracker from Pupil Labs with our modified hardware and software). The entire interaction will also be videotaped for off-line coding and scoring of language and validation of automatic measures of eye contact.

Analysis: Standard analyses will compare number and timing of instances of orienting to or disengaging from a directed social stimulus (repeated measures ANOVA comparing pre- and post-training measures and groups and interactions). More advanced analysis will use methods developed by [name]. Linguistic and Nonverbal communicative behaviors will be annotated into the Eudico Linguistic Annotator (ELAN) (Brugman, H., & Russel, A., 2004; Crasborn, O., & Sloetjes, H., 2008). ELAN, a video interface integrates behavioral data at millisecond resolution across multiple channels such as speech, eye gaze, head movement and facial expression. Behavioral states and discreet behaviors can be coded yielding frequency counts, total duration and mean duration as well as the coordination across channels, e.g., integrating an eye gaze shift in response to a question. These analyses include following behavioral categories: (i) Gaze: Location (target), Duration, Frequency; (ii) Head: position and movement; (iii) Speech (transcribed using CHILDES): utterances (content and length) and pauses.

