Level 3: The third level will test change in social behavior measured by questionnaires and a live social situation between the research participant and two testers. Trainees will be engaged in a three-way interactive conversation in which the testers use a scripted conversation and set of cues to direct attention and eye movement, videotaped for off-line coding and scoring. The script will involve several explicit and implicit redirections of attention and eye movement during the conversation between participants, using props in some cases to guide attention and gaze. We will work with our colleague and consultant on this project, [name], an expert in designing and analyzing this sort of interaction. [name] will ensure that the script and design are appropriate, the cameras are placed optimally for capturing the participants and that our plan for transcribing the interaction is sound and will reveal subtleties of social attention redirection. [name] will develop the coding system and will train students to score the videotapes.

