Standard analyses will compare number and timing of instances of orienting to or disengaging from a directed social stimulus (repeated measures ANOVA comparing pre- and post-training measures and groups and interactions). More advance analysis will use methods developed by [name]. Linguistic and Nonverbal communicative behaviors will be annotated into the Eudico Linguistic Annotator (ELAN) (Brugman, H., & Russel, A., 2004; Crasborn, O., & Sloetjes, H., 2008). ELAN, a video interface integrates behavioral data at millisecond resolution across multiple channels such as speech, eye gaze, head movement and facial expression. Behavioral states and discreet behaviors can be coded vielding frequency counts, total duration and mean duration as well as the coordination across channels, e.g., integrating an eye gaze shift in response to a question. Drs. [name] and [name] have developed methods for coding social behaviors in typical and atypical children and adults. These analyses include following behavioral categories: (i) Gaze: Location (target), Duration, Frequency; (ii) Head: position and movement; (iii) Speech (transcribed using CHILDES): utterances (content and length) and pauses. From these analyses, it is possible to determine the degree to which participants respond appropriately, both linguistically and behaviorally to social interactive cues. Novel analyses developed by [name] (a consultant on this project) use a recurrence technique in which the level of engagement of the participants is revealed in the pattern of their exchange (Figure 4). We will examine both speech and non-verbal indications of engagement, such as gaze and gestures. We will also obtain SRS scores to compare aspects of social engagement with a standardized assessment. This high level outcome measure allows us to examine the subtleties of visual and spoken engagement during a conversation. We expect that our intervention would promote more effective social interaction.

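### The plan makes no provision for masking the students who score the Level 3 videotapes to group or visit, which leaves the hand-coded social measures open to coder expectation

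*Combined protocol and SAP*

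**What the plan says.** Under Statistical Plan, Level 3, the live interaction is "videotaped for off-line coding and scoring". A consultant is to devise the coding scheme and "will train students to score the videotapes". The standard analysis concerns the "number and timing of instances of orienting to or disengaging from a directed social stimulus", tested by "repeated measures ANOVA comparing pre- and post-training measures and groups and interactions". Annotation in ELAN covers gaze, head movement and speech, and is meant to "determine the degree to which participants respond appropriately, both linguistically and behaviorally to social interactive cues". Gestures and engagement are also to be examined. The section closes with the team's expectation: "We expect that our intervention would promote more effective social interaction". The Social Interaction Task section ends with a similar expectation.

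The Social Interaction Task section describes the measurement differently. There, participant and tester both wear a lightweight eye-tracker that measures eye movements. Video has a supporting role: "The entire interaction will also be videotaped for off-line coding and scoring of language", and also validation of the automatic eye-contact measures. The Level 3 text in the Statistical Plan does not mention the tracker.

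Both sections name the SRS questionnaire as a further Level 3 measure. Neither section, nor any other part of the document, mentions masking of coders, coded file names or a shuffled scoring order.

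**The concern.** Deciding whether an orienting event occurred, when it began, or whether a reply was appropriate needs a person's judgement, even when the output is a count or a duration. A coder who knows that a tape was made after training, in a team that expects improvement, may score it more favourably. That would produce a pre-post change with no change in behaviour. If the coder also knows or guesses the group, the group-by-time interaction can be distorted in the same way.

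Level 3 is where the trial asks whether training carries over to social behaviour, and Aim 2 is to evaluate efficacy. A spurious positive result on the live-interaction codes would be read as evidence of that transfer. Because coding is done off-line from recordings, masking is easy to arrange, and the plan does not ask for it.

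**Working it through.** **The plan's own figure.** There is none to reproduce. The document gives no alpha, power, effect size or SD for Level 3.

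**Which measures are exposed.**

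| Level 3 measure | Source according to the document | Open to coder expectation? |
|---|---|---|
| SRS | Questionnaire | Not through tape coding |
| Eye movements | Worn tracker (Social Interaction Task) | No, if taken from the tracker |
| Orienting and disengaging events | Unclear: tracker (Social Interaction Task) or video (Statistical Plan, Level 3) | Yes, if coded from video |
| Language content, head movement, gesture, response appropriateness, engagement | Annotation of the recording; no automatic source is stated | Yes |

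**Which contrast is biased by what.** Suppose the true change is zero in both groups. Let unmasked coding add b1 to the change score in the gaze group and b2 in the joystick group.
- The pre-post contrast pooled over equal groups is shifted by (b1 + b2)/2. Knowledge of visit alone is enough.
- The group-by-time contrast is shifted by b1 − b2. If coders know only the visit, b1 = b2 and the shift is zero. A shift requires coders to know or guess the group.

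**Illustration of size.**

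Input from the document: 20 per group, 40 in total (Aim 1).

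Assumptions that are not in the document: two-sided alpha of 0.05; no true effect; a shift b of 0.25 to 0.5 SD of the change score in whichever contrast is examined.

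With noncentrality λ and critical value c, the false-positive rate is P(|T| > c), where T is noncentral t.

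- Group contrast: df = 38, c = 2.024, λ = b × √(20/2).
  - b = 0.25: λ = 0.25 × 3.162 = 0.791, rate 0.120.
  - b = 0.5: λ = 0.5 × 3.162 = 1.581, rate 0.338.
- Pooled pre-post contrast: df = 39, c = 2.023, λ = b × √40.
  - b = 0.25: λ = 0.25 × 6.325 = 1.581, rate 0.338.
  - b = 0.5: λ = 0.5 × 6.325 = 3.162, rate 0.869.

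With b = 0 both rates are the assumed 5%. For the same b, the pre-post contrast suffers more, and it is also the one that needs only knowledge of the visit.

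**The case against.** Several points on the other side stand, and they limit the claim.

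- **Silence is not evidence of unmasked coding.** A reader might infer that the students will know group and visit. The document does not say so: it describes neither file names, nor coding schedules, nor what coders are told. The interaction task has no group-specific version, so nothing shows that group is visible on tape. What the document supports is that no safeguard is provided.
- **Not all of Level 3 is hand-coded.** A reader might infer that every Level 3 result rests on student judgement. The Social Interaction Task section assigns eye movements to a tracker, and the SRS is not scored from tape. But that section also uses the video to validate the automatic eye-contact measures, and the Statistical Plan omits the tracker. The source of the orienting and disengaging counts is therefore unsettled.
- **The codes are structured.** ELAN counts, durations and transcribed utterances are less open to expectation than global ratings, so calling the scoring subjective throughout would go too far. Judgement remains in identifying and timing events, and above all in appropriateness and engagement.
- **The damage is recoverable.** A reader might infer that the bias would be permanent. If the recordings are kept, masked coders could rescore them, at the price of repeating the work.
- **This is a small pilot, and Level 3 is not named as primary.** That lowers the stakes. It does not remove the reason for a step that needs no extra staff.
- **Masked coding does not mask the live testers** who deliver the script. This is true, and it is a separate limit of what the fix below achieves.

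**Conclusion.** The concern holds for the hand-coded Level 3 measures: language content, head movement, gesture, response appropriateness and engagement, together with gaze events where these are coded from video. For these, the plan has students score the recordings, states the expected direction, tests pre-post and group differences, and provides no masking to group or visit. The pre-post contrast is the more exposed. The group-by-time contrast is at risk only if coders know or guess the group. The SRS and tracker-derived measures fall outside the point.

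The false-positive rates of about 12% to 34% (group) and 34% to 87% (pooled pre-post) show how sensitive the tests would be to a bias of 0.25 to 0.5 SD. A reader might take them as the expected error rates of this trial. The document does not support that, because it gives no information on the size of any coder bias. The recommendation rests on the missing safeguard and its low cost, not on those figures.

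**What to change.** In both the Social Interaction Task section and Statistical Plan, Level 3:

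1. Before coding, give each video a random code that hides the participant's group, the visit and the date. Have someone who does not code hold the key.
2. Present pre and post tapes of both groups in random order, once both of a participant's sessions have been recorded.
3. State that coders are masked to group and visit.
4. Reconcile the two sections on which Level 3 measures are automatic and which are hand-coded, and name the source of the orienting and disengaging counts.

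The cost is file renaming, a randomised coding list and a few sentences of text, with no extra staff. The small downside is that coding of a participant's tapes waits until the 8-week session has been recorded. If masking is already intended, items 3 and 4 are enough, together with a short description of how it is done.
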